#### **8.7 Adjustment of Dose and/or Treatment Schedule**

Dose frequency adjustments for platelet count reduction must be made in accordance with [Section 8.6.3](#) and [Table 3](#) (above).

Other dose adjustments, including dose interruptions, and/or decreasing the dose will be allowed for safety or tolerability in consultation with the Sponsor Medical Monitor.

Subjects may have their dose interrupted in response to AEs, and the Study Medical Monitor will be informed.

#### **8.8 Discontinuation of Study Drug/Treatment**

A subject must permanently discontinue study treatment for any of the following:

- The subject becomes pregnant. Report the pregnancy according to instructions in [Section 9.5.4](#)
- The subject withdraws consent
- The subject experiences an adverse event (AE) that necessitates permanent discontinuation of Study Drug
- The subject develops laboratory test abnormalities that meet any of the stopping rules listed in [Sections 8.6.1](#) to [8.6.3](#)
- When a platelet count of less than 50,000/mm^3, or a platelet count less than 75,000/mm^3 while the patient is on a reduced dose.

The reason for discontinuation of Study Drug Treatment must be recorded in the electronic Case Report Form (eCRF) and source documentation.

Subjects who discontinue treatment early should be entered into the post-treatment evaluation period. Every effort should be made to complete the early termination study procedures and observations at the time of withdrawal (see [Appendix A](#)).

If a subject discontinues treatment after only 1 dose, then the post-treatment evaluation procedures cohorts should be followed.

### **8.8.1 *Follow-up Visits for Early Termination from Treatment Period or from Post-Treatment Follow-up Period***

Any subject who discontinues early from the treatment period or from post-treatment follow-up period should be followed as per the platelet monitoring rules shown in, [Section 8.6.3](#) for the first 6 weeks after discontinuing Study Drug and then at 8 (weekly dosing cohort) or 10 (every 4 week dosing cohorts) and 13 weeks post end of treatment period (as per visit schedule).

If the subject declines or is unable to participate in the above, the early termination visit procedures should be performed at the time of withdrawal, at a minimum, and ideally within 2 weeks from the last dose of Study Drug.

### **8.9 *Withdrawal of Subjects from the Study***

Subjects must be withdrawn from the Study for any of the following:

- Withdrawal of consent
- The subject is unwilling or unable to comply with the protocol
- The subject meets any of the Exclusion Criteria (see [Section 5.2](#)) after enrolling in the study that in the opinion of the Investigator represents a safety risk to the subject

Other reasons for withdrawal of subjects from the Study might include:

- At the discretion of the Investigator for medical reasons
- At the discretion of the Investigator or Sponsor for noncompliance
- Significant protocol deviation

All efforts will be made to complete and report the observations as thoroughly as possible up to the date of withdrawal. All information, including the reason for withdrawal from Study, must be recorded in the eCRF.

Any subject who withdraws consent to participate in the Study will be removed from further treatment and study observation immediately upon the date of request. These subjects should be encouraged to complete the early termination study procedures and observations at the time of withdrawal ([Appendix A](#)).

For subjects withdrawn for reasons other than withdrawal of consent every effort should be made to complete the early termination (ET) study procedures and observations at the time of withdrawal (see [Appendix A](#)).

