## 5.2 Exclusion Criteria

1. Type 1 diabetes mellitus
2. Active chronic liver disease, alcoholic liver disease, Wilson's disease hemochromatosis, primary biliary cirrhosis, primary sclerosing cholangitis, genetic hemochromatosis, known or suspected hepatocellular carcinoma, history of or planned liver transplant for end-stage liver disease of any etiology
3. Documented history of advanced liver fibrosis
4. History of cirrhosis and/or hepatic decompensation including ascites, hepatic encephalopathy, or variceal bleeding
5. Uncontrolled hypertension (systolic > 160 or diastolic > 100 mm Hg)
6. History of acute kidney injury within 12 months of Screening
7. Active infection requiring systemic antiviral or antimicrobial therapy that will not be completed prior to Study Day 1
8. Subjects with a history of major bleed or high-risk of bleeding diathesis
9. Clinically-significant abnormalities in screening laboratory values that would render a subject unsuitable for inclusion, including the following:

- a. Positive test (including trace) for blood on urinalysis. In the event of a positive test, eligibility may be confirmed with urine microscopy showing  $\leq 5$  red blood cells per high power field
  - b. Urine protein/creatinine ratio (UPCR)  $\geq 0.25$  mg/mg. In the event of a UPCR above this threshold, eligibility may be confirmed by a quantitative total urine protein measurement of  $< 300$  mg/24-hr
  - c. Estimated GFR  $< 60$  mL/min/1.73 m^2 (as determined by the Chronic Kidney Disease-Epidemiological Collaboration (CKD-EPI) Equation)
  - d. Alanine aminotransferase (ALT) or aspartate aminotransferase (AST)  $> 2$  x ULN
  - e. Bilirubin  $> ULN$ , unless prior diagnosis and documentation of Gilbert's syndrome in which case total bilirubin must be  $\leq 3$  mg/dL
  - f. Alkaline phosphatase (ALP)  $> 1.5$  x ULN
  - g. Platelet count  $< LLN$
10. Known history of or positive test for human immunodeficiency virus (HIV), hepatitis C or chronic hepatitis B
  11. Uncontrolled hyper- or hypothyroidism. Subjects on dose stable replacement therapy for at least 3 months prior to Screening will be allowed
  12. History of clinically significant acute cardiac event within 6 months before Screening (includes stroke, transient ischemic attack, and coronary heart disease [angina pectoris, myocardial infarction, revascularization procedures])
  13. History of heart failure with NYHA greater than Class II

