## 8.5 Safety Monitoring Rules

Please refer also to the “Guidance for Investigator” section of the Investigator’s Brochure.

For the purposes of safety monitoring, Baseline is defined as the average of the pre-dose test closest to Day 1 and the Day 1 value itself.

In addition to the standard monitoring of clinical safety parameters, the following guidelines are provided for the monitoring of selected parameters chosen based on preclinical and clinical observations.

In case of discrepancy between the test results from 2 sources, such as between the central and local lab, safety-mandated action must be initiated based on the more critical (lower or higher, as relevant) of the 2 values.

**Confirmation Guidance:** At any time during the study (treatment or post-treatment follow-up periods), the clinical laboratory results meeting any of the safety monitoring criteria presented below **must be confirmed** by performing measurements (ideally in the same laboratory that performed the initial measurement) on new specimens prior to administering the next dose of Study Drug (ISIS 703802 or placebo). All new specimen collections should take place as soon as possible (ideally within 3 days of the initial collection).

In addition, as described in [Section 6.2](#) hematology labs should be sent in parallel to the central and local laboratory for analysis.

**Stopping Rule Guidance:** The Investigator may interrupt or permanently discontinue study treatment for any medical reason including changes in clinical laboratory results.

In the event of an initial clinical laboratory result that meets a stopping criterion, subjects must not be re-dosed until a confirmatory test result has been reviewed by the Study Medical Monitor. If any of the stopping criteria described below are met and are confirmed, the subject will be permanently discontinued from further treatment with Study Drug (ISIS 703802 or placebo), evaluated fully as outlined below and in consultation with the Study Medical Monitor or appropriately qualified designee, and will be entered into the post-treatment evaluation portion of the study. In general, subjects who do not meet the stopping rules based upon retest may continue dosing. However, the Investigator and the Study Medical Monitor (or appropriately qualified designee) should confer as to whether additional close monitoring of the subject is appropriate.

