#### **8.5.4 Safety Monitoring for Bleeding Events**

Subjects will be evaluated for occurrence of bleeding events continuously after the start of Study Drug treatment (Day 1) up to the end of the follow-up period for all cohorts. All bleeding events are considered adverse events and reported on adverse event case report form.

Bleeding events that are either major or clinically-relevant non-major bleeding (as defined below) will need to be monitored and treated immediately. Subjects with a suspected bleeding event will undergo additional testing if deemed appropriate by the treating physician and an (S)AE case report form will be completed. In addition, if bleeding is considered significant, hemoglobin (Hb), hematocrit (HCT), aPTT, PT, INR, and platelet count are to be obtained. In addition, approximately 2 mL of K2EDTA anticoagulated blood will be collected and resulting plasma must be stored allowing for a centralized assessment of ISIS 703802 concentrations.

In addition, if a minor bleeding event occurs, the Investigator should notify the Sponsor Medical Monitor (or designee) and additional testing of coagulation parameters (aPTT, prothrombin time [PT], INR), platelet count, and platelet volume may be performed.

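### Section 8.9 removes a subject from the Study, not only from Study Drug, when an emergent exclusion criterion is judged a safety risk; this is at odds with 8.8 and 6.1.3

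*Protocol*

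**What the plan says.** Protocol 8.9 opens with "Subjects must be withdrawn from the Study for any of the following". One of the listed reasons is that the subject meets any exclusion criterion "after enrolling in the study that in the opinion of the Investigator represents a safety risk to the subject". The risk judgement is the Investigator's; once it is made, withdrawal from the Study is not optional. For data, 8.9 asks sites to "complete and report the observations as thoroughly as possible up to the date of withdrawal". For withdrawals other than loss of consent it adds that "every effort should be made to complete the early termination (ET) study procedures and observations at the time of withdrawal". It asks for nothing later.

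Two other sections point the other way:

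- **8.8** lists an adverse event that requires a permanent stop among the reasons to discontinue Study Drug, and then says: "Subjects who discontinue treatment early should be entered into the post-treatment evaluation period".
- **6.1.3** plans safety follow-up of each subject for 13 weeks after the treatment period. Appendix A places visits at follow-up Weeks 4, 8 and 13.

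The exclusion criteria in 5.2 include "Subjects with a history of major bleed or high-risk of bleeding diathesis" (criterion 8), with no tie to Screening. Uncontrolled hypertension (5), hepatic decompensation (4) and malignancy (21) are likewise not tied to Screening.

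**The concern.** Stopping drug and leaving the Study are different acts. A subject who develops a new risk on treatment usually needs the first and has most to gain from avoiding the second. Section 8.9 joins them, while 8.8 and 6.1.3 keep them apart, and no rule of precedence is given. Two sites could treat the same event differently and each be following the protocol.

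What is at stake is mainly safety data: routine scheduled assessments in a subject who has just been judged at risk and still carries a drug with a long terminal half-life. A lesser stake is the completeness of the primary endpoint. SAP Appendix A assigns TG samples to the primary window by study day, so an off-drug follow-up sample can count. If it is never taken, the primary analysis imputes it as missing at random (SAP 3.3.1.2).

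**Working it through.** **1. One event, two routes.** Take a major bleed on treatment that leads to a permanent stop.

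- Under 8.8 it is an adverse event requiring discontinuation, so the subject enters the post-treatment period and, under 6.1.3, is followed for 13 weeks.
- Under 8.9 the subject now has a major bleed in their history (criterion 8). If the Investigator judges this a safety risk, the subject must leave the Study after ET procedures.

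Both descriptions fit, and no text chooses between them.

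**2. Length of the scheduled gap.** Appendix A, footnote q, ends the treatment period one dosing interval after the last dose (7 days in A, 28 days in B/C). Follow-up visits come 28, 56 and 91 days later. Section 8.8.1 gives within 2 weeks of the last dose as the ideal timing for a stand-alone ET visit, so ET is assumed at day 14.

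- A: last visit 7 + 91 = 98 days after the last dose; 98 − 14 = **84 days**.
- B/C: last visit 28 + 91 = 119 days; 119 − 14 = **105 days**.

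A later ET shortens the gap day for day, and an earlier one lengthens it.

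**3. Drug still present.** Protocol 2.3.4 gives a terminal half-life h of 3 to 5 weeks. The fraction of the terminal-phase component left after t weeks is 2^(−t/h).

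| t | h = 3 | h = 5 |
|---|---|---|
| 2 weeks (ET) | 0.63 | 0.76 |
| 14 weeks (last visit, A) | 0.04 | 0.14 |
| 17 weeks (last visit, B/C) | 0.02 | 0.09 |

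**4. TG values in the primary window.** The SAP windows are Days 156 to 183 (B/C) and 180 to 197 (A). Follow-up samples fall 56, 84 and 119 days after the last dose in B/C, and 35, 63 and 98 days after it in A.

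- B/C, last dose before an early stop on Day 1, 29, 57, 85 or 113. In window: 57 + 119 = 176, 85 + 84 = 169, 113 + 56 = 169. That is **3 of 5** (still 3 of 5 if every visit is 3 days early or late).
- A, last dose on Day 1, 8, …, 169 (25 points). In window: 85, 92, 99 (+98); 120, 127, 134 (+63); 148, 155, 162 (+35). That is **9 of 25** (6 of 25 if every visit is 3 days late, 9 of 25 if 3 days early).

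At these 12 points an ET sample within 14 days of the last dose is always too early. The latest cases are 113 + 14 = 127 < 156 and 162 + 14 = 176 < 180. The same holds for ET on the next due dose day: 113 + 28 = 141 < 156 and 162 + 7 = 169 < 180. ET reaches the window only if withdrawal comes at least 43 to 99 days (B/C) or 18 to 95 days (A) after the last dose, for instance after a dosing pause.

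**5. Power.** The stated 93% (difference 50, SD 46, 21 per arm, two-sided 0.05) reproduces at 93.0%. If completers fell to an assumed 19 or 17 per arm, it would be 90.3% or 86.7%.

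**The case against.** The strongest reply is that 8.9 stops observation at once only for subjects who withdraw consent; the paragraph on other withdrawals has no such words. Section 8.8.1 asks for platelet follow-up of any subject who discontinues early, with an ET visit alone as the fallback for those who decline or cannot take part. SAEs are followed to resolution (9.4.1), and liver, renal and other abnormal results carry their own follow-up (8.5.1, 8.6.2, 9.5.1). Criterion 8 also reads as an eligibility item about history, so a site may simply treat an on-study bleed under 8.8. All of this narrows the point. It does not remove it, because the event-driven rules need an abnormality to start them and no sentence tells the site that 8.8 governs.

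A reader might infer more than the documents support:

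- **That 8.9 also contradicts the stopping rules.** Section 8.5 says a subject with a confirmed stopping criterion "will be entered into the post-treatment evaluation portion of the study", but the matching exclusion (criterion 9) is limited to screening laboratory values.
- **That it contradicts 8.5.4.** Evaluating bleeding "up to the end of the follow-up period for all cohorts" is general surveillance, which any withdrawal would shorten.
- **That it contradicts glycaemic rescue.** Section 8.5.7 keeps rescued subjects on drug and in the Study, and 8.10.1.2 allows excluded drugs for a safety concern. That case is already settled.
- **That 63% to 76% of the drug level remains at 2 weeks.** Section 2.3.4 describes a multi-phasic decline with a rapid first phase, so the figure applies to the terminal-phase component only.
- **That bias in the TG result is shown.** The tallies count calendar points, not subjects, and Sensitivity Analysis 4 (SAP 3.3.1.3) partly covers active-arm subjects who leave for an adverse event.

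**Conclusion.** The concern holds in a limited form. Section 8.9 is at odds with 8.8 and 6.1.3 for a subject who meets an exclusion criterion on study that the Investigator judges a safety risk. Read literally, it can end routine scheduled follow-up for that subject. It does not end all monitoring.

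The size is 84 days (A) or 105 days (B/C) without scheduled chemistry, urinalysis, ECG, PK or antibody assessment. This assumes withdrawal during treatment, ET 14 days after the last dose, and a site that arranges no later visits of its own. Some off-drug TG values for the primary window may be lost as a secondary effect. How many subjects would be affected is unknown and could be none, and power is not at issue. The change is worth making because it is cheap and concerns subjects just judged at risk, not because lost data have been demonstrated.

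**What to change.** Replace the 8.9 bullet with text such as:

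> An exclusion criterion met after enrolment that the Investigator considers a safety risk is a reason to interrupt or permanently stop Study Drug. After a permanent stop, the subject enters post-treatment evaluation (Sections 8.8 and 8.8.1) and attends its scheduled visits, unless consent is withdrawn or the Investigator finds that continued observation is itself unsafe.

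A cross-reference to 8.5.7 is enough for rescued subjects. Stopping and rescue thresholds stay as they are.

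The cost is one reworded bullet with its cross-references, and a few subjects attending visits already in Appendix A. No new assessment is needed.

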### **8.10 *Concomitant Therapy and Procedures***

The use of concomitant therapies or procedures defined below must be recorded on the subject's eCRF. Adverse events related to administration of these therapies or procedures must also be documented on the appropriate eCRF.

### **8.10.1 Concomitant Therapy**

A concomitant therapy is any non-protocol specified drug or substance (including over-the-counter (OTC) medications, herbal medications and vitamin supplements) administered between Screening and the end of the post-treatment evaluation period. All concomitant medications/treatments and significant non-drug therapies (including supplements and assistive devices) received by a subject, including changes in the subject's current medications, must be recorded in the subject's source documents and CRF. Subjects taking over the counter omega-3 fatty acids should make every effort to remain on the same brand throughout the study.

#### **8.10.1.1 Allowed Concomitant Therapy**

Ibuprofen may be used for symptomatic pain relief. Any other therapy for pain (including OTC medications such as acetaminophen) should be approved by the Sponsor Medical Monitor or designee.

Any medications deemed necessary by the Investigator are allowed in response to an AE that requires drug therapy, except those listed in the disallowed concomitant therapy. In such cases, the Investigator must consult the Sponsor Medical Monitor to decide on subject continuation or withdrawal from the study.

#### **8.10.1.2 Disallowed Concomitant Therapy**

The use of prescription and OTC medications including nonsteroidal anti-inflammatory drugs (with the exception of occasional ibuprofen) is prohibited during this study unless the occurrence of an AE requires a drug therapy. In cases when there is no AE, the Investigator must consult the Sponsor Medical Monitor to decide on subject continuation or withdrawal from the study.

The medications and therapy identified in exclusion criteria, [Section 5.2](#) are also disallowed concomitant medications and are prohibited during the course of study, unless there is a safety concern. In those cases, the Medical Monitor needs to be notified and rationale provided by the Investigator.

Concomitant therapy with oral corticosteroids used as replacement therapy for pituitary adrenal disease as well as inhaled steroid therapy (e.g., Pulmicort®), or intra-articular, or topical may be acceptable; however, the subject must be on a stable regimen for at least 4 weeks prior to Screening. All exceptions should be discussed with the Sponsor Medical Monitor.

Subject should consult with the Site Investigator or designee prior to initiating any new medication, including non-prescription or herbal compounds or any other non-drug therapy.

### **8.10.2 Concomitant Procedures**

A concomitant procedure is any therapeutic intervention (e.g., surgery/biopsy, physical therapy) or diagnostic assessment (e.g., blood gas measurement, bacterial cultures) performed between Screening and the end of the post-treatment evaluation period.

## **8.11 Treatment Compliance**

Compliance with treatment dosing is to be monitored and recorded by Study Center staff. The Study Center staff is required to document the receipt, dispensing, and return/destruction of

study medication. Subjects that are self-administering study medication at home must record treatment in a dosing diary that will be reviewed periodically by Study Center staff and the Clinical Monitor.

## **9. SERIOUS AND NON-SERIOUS ADVERSE EVENT REPORTING**

### **9.1 Sponsor Review of Safety Information**

Safety information will be collected, reviewed, and evaluated by the Sponsor or designee in accordance with the Safety Management Plan throughout the conduct of the clinical trial.

### **9.2 Regulatory Requirements**

The Sponsor or designee is responsible for regulatory submissions and reporting to the Investigators of serious adverse events (SAEs) including suspected unexpected serious adverse reactions (SUSARs) per the International Conference on Harmonization (ICH) guidelines E2A and ICH E6. Country-specific regulatory requirements will be followed in accordance with local country regulations and guidelines.

Institutional Review Boards (IRB)/Independent Ethics Committees (IEC) will be notified of any SAE according to applicable regulations. The Data and Safety Monitoring Board (DSMB) will be notified of any SAE as specified in the DSMB charter.

In addition to the Investigator's assessment of relatedness, the Sponsor or designee will evaluate the available information and perform an independent assessment of relatedness. While the Sponsor may upgrade an Investigator's decision, it is not permissible to downgrade the Investigator's opinion for the purposes of determining whether the SAE meets the definition of a SUSAR.

Appropriate personnel at the Sponsor or designee will unblind SUSARs for the purpose of regulatory reporting. The Sponsor or designee will submit SUSARs to Regulatory Agencies in blinded or unblinded fashion according to local regulation. The Sponsor or designee will submit SUSARs to Investigators in a blinded fashion.

For the purpose of regulatory reporting of SUSARs, there are no "expected" AEs in this study population. For Study Drug (ISIS 703802 or placebo) "expected" AEs, refer to the Investigator's Brochure.

### **9.3 Definitions**

#### **9.3.1 Adverse Event**

An adverse event is any unfavorable and unintended sign (including a clinically significant abnormal laboratory finding, for example), symptom, or disease temporally associated with the study or use of investigational drug product, whether or not the AE is considered related to the investigational drug product.

